10.6 Pregnancy

Male subjects who are sexually active with a female partner of child-bearing potential must agree to use a condom for the duration of participation in the study and for 30 days after the last dose of study medication.

However, if the partner of a male study subject becomes pregnant during the subject's participation in the study and for up to 30 days after the last dose of IMP, this should be reported to the investigator. Consent will be sought from the partner and, if granted, any pregnancy will be followed and the status of mother and/or child will be reported to the sponsor after delivery.

10.7 Data Safety Monitoring Board

A DSMB will be convened with the primary remit of providing independent safety oversight of the study. The composition of the DSMB, its terms of reference and its operating procedures will be described in the DSMB Charter which will be finalised before the first subject is randomised into the study.

The DSMB may, at any time, make recommendations to the NeRRe Chief Medical Officer of changes to the conduct of the study, including temporary or permanent discontinuation of the trial, to ensure the benefit-risk balance to participants remains appropriate. The default assumption is

Protocol No.: ORV-PF-01 Final V4.0 (US) Page 53 of 85

CONFIDENTIAL Protocol No.: ORV-PF-01
NeRRe Therapeutics Ltd

that DSMB recommendations will be implemented by the Sponsor, although exceptionally there may be further consultation with third parties (for example regulatory agencies) before changes to study conduct are implemented.

Protocol No.: ORV-PF-01 Final V4.0 (US) Page 54 of 85

Product:

ORVEPITANT

11. STATISTICAL CONSIDERATIONS

11.1 General Statistical Considerations

Subjects will be randomised to cohort and then further randomised to treatment order.

The primary objective of the study is to evaluate the effect of orvepitant once daily on cough severity, as perceived by patients, with IPF. The corresponding primary endpoint is the mean change from Baseline to Week 4 (the last 7 days of treatment) in weekly average of the daily IPF Coughing Severity Scale score.

The primary objective will be assessed by testing the following hypotheses for each orvepitant dose group separately:

Null hypothesis (H0): There is no difference in the mean change in mean IPF Coughing Severity Scale scores for the orvepitant treatment group compared to placebo.

H0: μ (active) = μ (placebo)

Alternative hypothesis (H1): There is a difference in the mean change in mean IPF Coughing Severity Scale scores for the orvepitant treatment group compared to placebo.

H1: μ (active) $\neq \mu$ (placebo)

Each comparison will be carried out at the two-sided 5% level of statistical significance. No adjustment will be made for the multiple orvepitant versus placebo group comparisons in this phase 2 study (two in total: 10 mg versus placebo, 30 mg versus placebo) as each dose cohort is tested independent (versus the corresponding placebo) and each is adequately powered.

11.1.1 Definition of Baseline

Baseline values will be defined separately for each treatment period, unless stated otherwise.

For the primary efficacy endpoint, period-specific baseline will be used in the analysis, which is the average of the 7 calendar days up to and including the date of Visit 2 for Treatment Period A and the average of 7 calendar days up to and including the date Visit 5 for Treatment Period B.

For secondary efficacy endpoints related to change from baseline, the period-specific baseline will be used when available; for those endpoints for which a period-specific baseline is not available (cough frequency and Hull Airway Reflux Questionnaire), the baseline in Treatment Period A will be used.

For safety assessments, baseline will be Visit 2 for Treatment Period A and for Treatment Period B it will be Visit 5.

For both safety and efficacy assessments, if the period-specific baseline is missing for Treatment Period A the value from Visit 1 will be used. If this is missing change from baseline will not be calculated. If the period-specific baseline is missing for Treatment Period B the value from Visit 2 (first preference) or Visit 1 (second preference) will be used. If both are missing change from baseline will not be calculated.

11.2 Carry Over Effects

A potential limitation of any cross-over study is the occurrence of confounding carry over effects between treatment periods. The wash-out period for this study is 3-weeks which, given that the half-life of orvepitant is approximately 33 hours, is expected to be sufficient for the drug to be fully cleared and for cough symptoms to return to baseline levels.

Protocol No.: ORV-PF-01 Final V4.0 (US) Page 55 of 85

Period-specific baseline values will be used in the analysis of primary and secondary efficacy endpoints, and safety endpoints, when available, to protect against possible carryover effect.

11.3 Estimated Sample Size

Assuming a common standard deviation of 2.7 for the difference between treatment periods, a sample size of 40 subjects per cohort (18 -19 per sequence) has 90% power if the difference between treatments on the IPF Coughing Severity Scale is 1.5 points and assuming a two-sided type I error of 0.05, not adjusted for multiple comparisons. To allow for non-evaluable subjects/ missing data the withdrawal rate and extent of missing data will be monitored as the trial progresses and the actual sample size will be increased accordingly such that data is available for 37 evaluable subjects.

As there have been no previous studies using NRS for cough severity the standard deviation of 2.7 was obtained based on historical data of the change in cough severity measured using VAS. A 2-week observational study has since been completed in which the standard deviation of the change from baseline in NRS was 1.45 (95% CI: 1.14 - 2.01). Using the upper bound of the 95% CI and applying an inflation factor of 1.3 (derived from the observed increase in standard deviation from week 2 to week 12 in the historical VAS study data) resulted in an estimated standard deviation of 2.6. As this is very similar to, and lower than, the standard deviation originally used in the sample size estimation the estimated sample size required was not updated.

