- f. The use of other NK₁ antagonists (eg aprepitant, fosaprepitant, rolapitant) is not permitted for any reason from 4 weeks before the Baseline visit until completion of Visit 8
- g. Immune-suppressant drugs and systemic corticosteroids taken for co-morbidities are permitted provided the dose has been stable for at least 2 weeks before the screening visit and they are expected to be used at this dose throughout the study. Any other use is prohibited
- h. Supplemental oxygen is permitted provided it has been used for at least 2 weeks before the screening visit and is expected to be used throughout the study
- 13. Participation in any clinical research study evaluating another investigational drug or therapy within 30 days or within 5 half-lives (whichever is longer) of the investigational drug prior to Screening. If the subject was in an observational clinical study, no washout is required
- 14. Subjects who have previously received orvepitant at any time
- 15. Known allergy to any of the excipients used in the investigational medicinal product (IMP) (orvepitant or placebo tablets)
- 16. Subjects who, in the opinion of the Investigator, should not participate in the study for any other reason
- 17. Subjects who are dependent on the Sponsor, CRO or investigator for employment of education

PATIENT REPORTED OUTCOMES DEVELOPMENT AND VALIDATION

After completing Visit 7, a subgroup of patients from sites in all participating countries will be invited to take part in detailed cognitive debriefing interviews. These interviews form part of the

Protocol No.: ORV-PF-01 Final V4.0 (US) Page 9 of 85

ongoing development and validation of the patient reported outcomes being used to assess burden of cough.

burden of cough.			
STATI	STATISTICAL CONSIDERATIONS		
PLANNED SAMPLE SIZE	Assuming a common standard deviation of 2.7 for the difference between treatment periods, a sample size of 37 subjects per cohort (18-19 per sequence) has 90% power if the difference between treatments on the IPF Coughing Severity Scale is 1.5 points and assuming a two-sided type I error of 0.05, not adjusted for multiple comparisons. To allow for non-evaluable subjects/missing data, the withdrawal rate and extent of missing data will be monitored as the trial progresses and the actual sample size will be increased accordingly such that data is available for 37 evaluable subjects		

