7.1 Subject numbers

In the first instance, approximately 88 subjects will be recruited into the study in two equal sized cohorts.

Protocol No.: ORV-PF-01

The number of subjects enrolled may be increased to a maximum of 108 if the interim sample size re-estimation indicates that 88 is insufficient (see Section 11.3).

Subjects will be enrolled at approximately 30 sites across North America and Europe. Additional sites and regions may be added.

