**Figure 1. Study Schematic** 

### 2.5 STUDY SAMPLE SIZE DETERMINATION

# 2.5.1 Estimated Sample Size

Assuming a common standard deviation of 2.7 for the difference between treatment periods, a sample size of 37 subjects per cohort has 90% power if the difference between treatments on the cough severity NRS is 1.5 points and assuming a two-sided type I error of 0.05, not adjusted for multiple comparisons. To allow for non-evaluable subjects/missing data the withdrawal rate and extent of missing data will be monitored as the trial progresses and the actual sample size will be increased accordingly such that data is available for 37 evaluable subjects.

As there have been no previous studies using NRS for cough severity the standard deviation of 2.7 was obtained based on historical data of the change in cough severity measured using VAS. A 2-week observational study has since been completed in which the standard deviation of the change from baseline in NRS was 1.45 (95% CI: 1.14 - 2.01). Using the upper bound of the 95% CI and applying an inflation factor of 1.3 (derived from the observed increase in standard deviation from week 2 to week 12 in the historical VAS study data) resulted in an estimated standard deviation of 2.6. As this is very similar to, and lower than, the standard deviation originally used in the sample size estimation the estimated sample size required was not updated.

The proposed clinically relevant improvement of 1.5 points in the IPF coughing severity scale is an initial estimate based on the findings from the qualitative interviews with IPF patients conducted during the observational study. The qualitative interviews and psychometric analyses being undertaken as part of the current study will confirm (or else amend) this change for use in future studies.

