### 2.6 TREATMENT ASSIGNMENT AND BLINDING

### 2.6.1 Randomisation

Subjects will be randomised on Day 0 in a 1:1 ratio to either Cohort 1 or Cohort 2, and then within each cohort will be further randomised in a 1:1 ratio to receive either placebo or orvepitant in Treatment Period A. Randomisation will be performed centrally via an IWRS. The central randomisation list will be generated by using SAS 9.4 (SAS Institute Inc., Cary, North Carolina, United States of America) or higher.

Page 11 of 50

<sup>2 VOLCANO-2 (A double blind, randomised, placebo controlled study of the efficacy and safety of three doses of orvepitant in subjects with chronic refractory cough), clinical study report, 09 Apr 2020.

<sup>3 IPF-Obs-01 (An observational study to record cough symptom severity in patients with chronic cough due to idiopathic pulmonary fibrosis), clinical study report, 20 Sep 2021.

<sup>4 The sample size re-estimate has been completed using data from 25 subjects and showed that the variance was not greater than that assumed variance in the original calculation. The required number of evaluable subjects per cohort therefore remains 37.

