# Table Template 1: Blinded Sample Size Re-estimation [1]

Number of Subjects in Both Cohorts with Evaluable Data [2] (N=XX)

Data as of: dd-mmm-yyyy

Type of Estimate	Standard	Sample Size
	Deviation of	Estimate per
	Paired	Cohort
	Difference	
Protocol-Specified	2.7	XX
Point Estimate	XX.XX	XX
80% Confidence Interval of Point Estimate [3]		
Lower Bound	XX.XX	XX
Upper Bound	XX.XX	XX
Estimates derived from Robust Measures of Scale [4]		
Interquartile Range / 1.34898	XX.XX	XX
Gini's Mean Difference * sqrt(pi)/2	XX.XX	XX
MAD * 1.4826	XX.XX	XX
Sn * Csn	XX.XX	XX
Qn * Cqn	XX.XX	XX

Pi is the numerical constant that represents the ratio of a circle's circumference to its diameter.

[figure not shown]
MAD is Median absolute deviation about the median (Hampel; 1974).

Sn and Qn are robust estimators proposed by Croux 1992. Csn and Cqn are correction factors used to estimate the standard deviation from Sn and Qn, respectively.

- [1] Sample size estimates per cohort assume a treatment difference=1.5, two-sided alpha=0.05, and 90% power using a paired t-test.
- [2] A subject is evaluable if they were randomized and received treatment and the primary endpoint can be computed for both treatment periods.
- [3] This confidence interval assumes (n-1)\*Vhat/V is chi-square with n-1 df, where Vhat and V are the variance estimate and the variance parameter, respectively.
- [4] See SAS documentation for the ROBUSTSCALE option of PROC UNIVARIATE.

Page 49 of 50

**Figure Template 1: Distribution and Probability Plot of the Blinded Paired Differences** Number of Subjects in Both Cohorts with Evaluable Data [2] (N=XX) Data as of: dd-mmm-yyyy

[1] A subject is evaluable if they were randomized and received treatment and the primary endpoint can be computed for both treatment periods.

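### Protocol 11.3 attaches 90% power to 40 subjects per cohort, but its own inputs, its per-sequence split, the synopsis and the SAP all give 37

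*Protocol*

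**What the plan says.** Protocol 11.3 gives the sample size justification as "a sample size of 40 subjects per cohort (18 -19 per sequence) has 90% power". The inputs around it are an SD of 2.7 for the difference between periods, a treatment difference of 1.5 points on the IPF Coughing Severity Scale, and two-sided alpha of 0.05 without multiplicity adjustment. No test is named. The paragraph ends by saying that recruitment will be adjusted so that "data is available for 37 evaluable subjects".

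The other statements of the same calculation read differently:

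- Protocol synopsis, planned sample size (same inputs, same bracket): "a sample size of 37 subjects per cohort (18-19 per sequence) has 90% power".
- SAP 2.5.1: "a sample size of 37 subjects per cohort has 90% power".
- SAP footnote 4, attached to 2.5.2 and reporting the completed blinded re-estimation: "The required number of evaluable subjects per cohort therefore remains 37".

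The SAP names the test in the notes to Table Template 1 (section 14.2), where the sample size estimates "assume a treatment difference=1.5, two-sided alpha=0.05, and 90% power using a paired t-test".

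On recruitment, Protocol 7.1 says "approximately 88 subjects will be recruited into the study in two equal sized cohorts", and that the number "may be increased to a maximum of 108 if the interim sample size re-estimation indicates that 88 is insufficient".

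**The concern.** The figure beside the power claim in the protocol's formal sample size section should be the figure that the stated inputs produce. Here it disagrees with the bracket in its own sentence, with the evaluable target in the next sentence, with the synopsis of the same protocol version, and with the SAP.

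The protocol thus carries three per-cohort numbers: 40 in 11.3, 37 in 11.3 and the synopsis, and 44 implied by 7.1. It does not say how they relate. A reader has to infer that 37 is the calculated requirement and 44 the recruitment plan, and has no role left for 40. What is at stake is whether the justification can be reproduced, not whether the trial is adequately powered.

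**Working it through.** **Inputs.** Difference 1.5, SD of the paired difference 2.7, two-sided alpha 0.05, power 90% (Protocol 11.3); paired t-test (SAP 14.2); 1:1 allocation to treatment order (Protocol 8.6).

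**Formula.** With noncentrality λ = 1.5·√n / 2.7 and critical value t* = t(0.975, df), power = 1 − F(t*; df, λ) + F(−t*; df, λ), where F is the noncentral t distribution function. The paired t-test has df = n − 1. A crossover analysis that also fits a period effect has df = n − 2, so both are shown.

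| n per cohort | λ | Power, df = n − 1 | Power, df = n − 2 |
|---|---|---|---|
| 35 | 3.287 | 0.8911 | 0.8906 |
| 36 | 3.333 | 0.8998 | 0.8993 |
| 37 | 3.379 | 0.9079 | 0.9075 |
| 38 | 3.425 | 0.9154 | 0.9150 |
| 40 | 3.514 | 0.9287 | 0.9283 |
| 44 | 3.685 | 0.9497 | 0.9495 |

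The 37 in the synopsis and SAP is reproduced: it is the smallest n at or above 90% under either choice of df, and 36 just misses (89.98%). The 40 is not reproduced.

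**Could another method give 40?**

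- Normal approximation: (1.960 + 1.282)² × (2.7/1.5)² = 34.04 with unrounded quantiles, so 35.
- SD 2.6, the updated estimate mentioned in 11.3: 34.
- Two-sided alpha 0.025: 43.
- One-sided alpha 0.05: fewer than 34, where power is already 93.7%.
- 2.7 read as the within-subject SD, so that the SD of the difference is 2.7 × √2 = 3.82: 71.
- Two independent groups: 69 per group.

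None gives 40. For 40 to have exactly 90% power, the SD would have to be about 2.85 (difference 1.5) or the difference about 1.42 (SD 2.7). Neither value is stated.

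**The bracket.** 18 + 18 = 36, 18 + 19 = 37, 19 + 19 = 38. At 1:1, 40 needs 20 + 20. The printed split fits 37 and excludes 40.

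**Could 40 be a recruitment figure?** Protocol 7.1 recruits 88/2 = 44 per cohort. Its ceiling of 108 equals 88 + 2 × 10, the 10 per cohort being the re-estimation allowance in Protocol 11.3.1. Starting from 40 per cohort the ceiling would be 80 + 20 = 100. As allowances for loss, 40 would imply 1 − 37/40 = 7.5% and 44 implies 1 − 37/44 = 15.9%; the documents state neither rate.

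**The case against.** The strongest reply is that the sentence is not false: 40 subjects do have at least 90% power. That is true of sufficiency. But the paragraph presents an estimate of the number required, and the bracket and evaluable target beside it belong to 37.

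A second reply is that the intended figure is easy to work out, because the surrounding text and the SAP all point to 37, and Protocol 11.6 lets the SAP prevail where statistical analysis text differs. The first part is fair and limits the harm. The precedence clause concerns analysis text, and whether it reaches a sample size statement is arguable. In any case it does not repair a disagreement between two parts of the protocol.

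A third reply concerns versions. The SAP rests on protocol V3.0/3.1 and the protocol is V4.0, so 40 might be a later change. The documents do not show where the 40 came from, and an incomplete edit cannot be excluded. But the V4.0 synopsis and the V4.0 evaluable target still say 37, and 11.3 itself reports that the estimate was left unchanged after the observational study.

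Two smaller points stand. The SAP documents the paired t-test for the re-estimation rather than expressly for the original calculation, although Table Template 1 has a row applying it to the protocol's SD of 2.7. And the evaluable target in 11.3 does not itself say per cohort; SAP footnote 4 does.

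**Conclusion.** The concern holds, at low priority. On the stated inputs and a paired t-test the requirement is 37 evaluable subjects per cohort (90.8% power). The printed 40 is three subjects too many for a 90% claim and corresponds to 92.9%. The choice between n − 1 and n − 2 degrees of freedom does not affect this, and none of the alternative methods tried yields 40.

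The error is conservative. Planned recruitment of 44 per cohort exceeds both figures, and the blinded re-estimation has already been completed with 37 retained. Power, enrolment, the evaluable target and the analysis are unaffected. What is wrong is one number in the section that is meant to justify the sample size.

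**What to change.** In Protocol 11.3, change 40 to 37 and leave the bracket as it is. It would help to name the paired t-test there and to add per cohort to the evaluable target, so that the calculation can be reproduced from the protocol alone.

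If 40 was intended as a recruitment number, detach it from the power claim and the per-sequence split, label it as recruitment, state the loss it allows for, and reconcile it with the 88 and 108 in Protocol 7.1.

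The cost is an editorial correction of one number. The SAP figures need no change.

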11.3.1 Sample size re-estimation

After at least 12 subjects in each cohort have completed Treatment Period B, the variance of the IPF Coughing Severity Scale data will be reviewed on a fully blinded basis. Additional subjects (up to a maximum of 10 per cohort) may be recruited if the emerging IPF Coughing Severity Scale data is found to have greater variance than allowed for in the original sample size estimate. Any possible impact on the type I error due to this blinded sample size re-assessment procedure is believed to be negligible [45].

11.4 Estimand

The primary **objective** of the study is to evaluate the efficacy of orvepitant as a treatment for chronic cough in patients with IPF.

The **treatment of interest** is orvepitant (at a dose of 10 or 30 mg once daily). The effects of orvepitant will be compared to placebo.

The **population** is patients with IPF and troublesome chronic cough in whom the cough is attributed to the IPF.

The main variable being used to assess the estimand is the IPF Coughing Severity Scale.

The estimand will be **summarised** by comparing the mean changes from baseline in weekly cough severity score for the orvepitant treatment period versus the placebo treatment period.

Intercurrent events that are expected to occur during the study are initiation of concomitant medication, withdrawal from study treatment, withdrawals from the study due to death.

A treatment policy strategy will be used for the initiation of concomitant medication as well as for early withdrawal from study treatment, essentially following the intention to treat principal. Any patients who discontinue treatment early will be followed up until the end of the study, with the aim of collecting all scheduled data.

Protocol No.: ORV-PF-01 Final V4.0 (US) Page 56 of 85

A while on-treatment strategy will be used for withdrawal from the study due to death. All data for any subjects who die will be included up to the point of their withdrawal or death and no imputation will be made for any visits that may have occurred after the intercurrent event.

The estimand can then be defined as the difference between orvepitant and placebo in the change from baseline in weekly IPF Coughing Severity Scale score, measured using an NRS, in patients with IPF and troublesome chronic cough in whom the cough is attributed to the IPF, regardless of their need for concomitant medications or whether they discontinue study treatment, up until they complete the study, withdraw from the study or die (whichever comes first).

11.5 Analysis Sets

The following data sets will be used for the statistical analysis.

- 1. **Safety Set**: All subjects who receive at least one dose of double-blind study drug irrespective of treatment received. Subjects will be analysed according to treatment received
- 2. Full Analysis Set (FAS): All randomised subjects who received at least one dose of double-blind study drug, irrespective of treatment received, and have sufficient IPF Coughing Severity Scale data for at least one post-treatment assessment. Subjects will be analysed according to randomised treatment. This is the primary efficacy analysis set for the study.
- 3. **Per Protocol (PP) Set**: All subjects in the FAS excluding those identified as having a relevant protocol violation, where a relevant violation is one that potentially confounds the analysis of the primary efficacy endpoint.
- 4. **Exposure-Response (ER) Set:** all subjects who received at least one dose of double-blind study drug and for whom the PK data are considered sufficient.

Analysis Sets will be agreed at a blinded data review meeting prior to the unblinding of the study.

